6.2 Description of Evaluations

All activities in this study (except for biochemical validation) will occur online or via telephone. The ASHLine 2.0 system and/or REDCap data base will be used to automate, deliver and track all study-related activities. The ASHLine 2.0 system or REDCap will provide the prompts and scripts for ASHLine or study staff to describe the study, screen for eligibility, read the abbreviated informed consent document, obtain and document informed consent, obtain and document the baseline assessment and confirm and document consent. The REDCap system will perform and track randomization, assign participant to study coach, and track all follow-up assessments.

Table 3 above shows the schedule of assessments. Baseline assessments will be administered by ASHLine or study staff via phone as per "Visit 0". All participants will be administered the Treatment Administration Form which will document their participation in the telephone coaching calls during Visits 1 to 6. Use of the websites will be collected automatically. Eight-week and 6-month assessments will be conducted by study staff. Links to online surveys will be sent via email, with reminder calls and emails for up to four weeks. Surveys can be completed online or via phone with study staff. Biochemical validation will be done on all participants who report abstinence on the 6-month assessment and agree to perform a saliva test monitored via video chat by study staff.

6.2.1 Screening Evaluation

Smokers who express interest in our study will eligible if they:

- Have smoked any cigarettes in the past 30 days.
- Are willing to quit smoking within 30 days.
- Want help / information about quitting.
- Are not currently receiving any type of tobacco cessation treatment.
- Are at least 18 years of age.
- Have not enrolled and participated in Quitline services in the past 12 months.
- Have never been diagnosed with schizophrenia by a health care professional.
- Have current valid email address.
- Are willing to receive occasional text messages from us.

Consenting Procedure

The potential participants who are eligible to participate in the study will be read the abbreviated informed consent document verbatim by ASHLine or study staff. The abbreviated and full informed consent documents and the study were reviewed and approved by the University of Arizona IRB prior to recruitment.

Participants are called by study staff to confirm consent and are then emailed the full

informed consent and are told that if after reading the full consent they decide not to participate to inform study staff.

All ASHLine and study staff are trained in Human Subjects Protection and the Responsible Conduct of Research. ASHLine staff are employed by the College of Public Health and regularly participate in recruitment for research studies. The PI will train the ASHLine and study staff in the procedures for the study and ensure that all staff demonstrate understanding before they begin enrolling participants.

All procedures and systems will be thoroughly tested prior to implementation. ASHLine and study staff will be instructed to inform the PI or [name] if they experience problems using the informed consent document or the ASHLine 2.0 and REDCap systems. If any study procedures affecting participants change, appropriate changes will be made to the informed consent document and resubmitted to the University of Arizona IRB for approval.

ASHLine or study staff will read the abbreviated informed consent document as many times as requested by the caller. The caller will provide verbal consent which will be documented in the ASHLine 2.0 or REDCap system. Study staff will send an email of the full-length informed consent document to each participant for their records.

Screening

All screening will be performed at the time of the first call to the ASHLine (Visit 0). Participants will be eligible if they:

- Have smoked any cigarettes in the past 30 days.
- Are willing to quit smoking within 30 days.
- Want help / information about quitting.
- Are not currently receiving any type of tobacco cessation treatment.
- Are at least 18 years of age.
- Have not enrolled and participated in Quitline services in the past 12 months.
- Have never been diagnosed with schizophrenia by a health care professional.
- Have current valid email address.
- Are willing to receive occasional text messages from us.

At any time, if the caller is not eligible, staff will inform the caller that they are not eligible to participate in the study and will offer standard ASHLine coaching.

6.2.2 Enrollment, Baseline, and/or Randomization

Enrollment

Enrollment in the study will occur upon completion of the informed consent document, the baseline assessment, confirmation of consent and randomization to one of the study conditions. All screening, consent, assessment and randomization activities will be prompted and tracked by the ASHLine 2.0 system and REDCap data base.

Assessments

All of the measures proposed for use in this study have been used successfully in our previous work. All baseline assessments will be administered by ASHLine or study staff. See Table 4.

Measures for All Participants

Demographics. At baseline, we will collect gender, age, race/ethnicity, level of education, insurance, prior use of tobacco cessation resources (including quitline and medication) and guided mental imagery experience.

Tobacco use. At baseline, at every session, 8-weeks and 6-months post-enrollment, we will collect tobacco use status using a series of questions that have been standardized and employed in previous studies (Severson, [name], et al., 2008, [name] et al., 2007; Severson et al., 2000), and level of dependence using the the Fagerström Tolerance Nicotine Dependence scale (Fagerstrom & Schneider, 1989). We will conduct

Table 4. Measures			
Both Conditions	T0	T1	T2
Demographics	✓		
Tobacco Use	✓	✓	✓
Dependence	✓	✓	✓
Cravings	✓	✓	✓
Self-Efficacy	✓	✓	✓
Expectancy/Credibility	✓	✓	✓
Biochemical Validation			✓
Consumer Satisfaction		✓	
Website Use		Dai	ly
Intervention Only	Daily	T1	T2
Imagery File Use	✓		
Imagery Mastery	✓		

biochemical validation using a saliva test kit on all participants who report abstinence at the 6-month assessment and agree to perform a saliva test. Participants meeting these criteria will be mailed a saliva kit in the mail and then join a video chat with staff who will instruct the participant and monitor the collection of saliva and reading of the test strip. Participants will be offered \$25 for completing the saliva assessment. As all participants will be current smokers, there is no need for biochemical testing at baseline.

Self-efficacy for quitting. We will measure self-efficacy for quitting smoking with items from the 15-item version of the Condiotte & Lichtenstein Confidence Questionnaire (Condiotte & Lichtenstein, 1981).

Cravings. All participants will be asked to rate their experience with withdrawal symptoms and cravings using items from the 5-item Shiffman rating scale (Shiffman, 2004) at each baseline and each follow-up assessment.

Imagery expectancies and credibility. We will include items adapted from the Borokov and Nau (1972) Treatment Credibility Scale, and used in our on-going guided imagery mobile app study, to measure expectancies and perceived credibility of guided imagery for smoking cessation.

Consumer satisfaction measure. At both follow-ups, participants will complete a consumer satisfaction survey that we have used in our previous research ([name] et al., 2013; Severson, [name], et al., 2008) consisting of 8 items (using a 5-point Likert scale), measuring overall satisfaction with the program, perceived usefulness and relevance of the information, likeability, level of interest, ease of use, and whether they

Commented [PG-(2]: Note that the checkmark for T1 has been removed.

would recommend the program to others.

Website use. We collect usage data and can analyze use of all components of the site. Data most likely related to outcome will include, but not be limited to: (a) the length of time participants interact with the site; (b) the number of pages they visit within the site, and (c) the number of links they click on while using the site.

System usability. At both follow-up assessments, we will use Tullis and Stetson's (2008) 10-item adaptation of Brooke's widely used System Usability Scale (Brooke, 1996) to rate the usability of our website.

Measures for Only Imagery Intervention Condition Participants

Imagery files use. We will collect number of times imagery files were listened to , and if the participant modified or created their own file.

Imagery mastery. Ratings of imagery vividness and controllability will be measured weekly via the coach in order to verify compliance with the protocol (Marks, 1973).

Randomization

Eligible participants who are consented and complete the baseline assessment will be automatically randomized immediately by the REDCap system using a randomization algorithm. The assignment will be documented and tracked in the REDCap system, and the participant will be assigned to a study coach.

6.2.3 Blinding

Due to the nature of the study with two different behavioral interventions it would not be possible to blind participants or study coaches.

6.2.4 Follow-up Visits

All measures by follow-up are listed in Table 3. There will be two follow-up assessments: 1) 8 weeks post-enrollment; and 2) 6 months post-enrollment. All items will be asked at each follow-up assessment of every participant. In addition, biochemical validation of self-reported tobacco use will be conducted on all participants who report abstinence at the 6-month assessment and agree to perform a saliva test. Participants meeting these criteria will be mailed a saliva kit in the mail and then join a video chat with staff who will instruct the participant and monitor the collection of saliva and reading of the test strip. Participants will be offered \$25 for each sample.

6.2.5 Completion/Final Evaluation

The items assessed at the final follow-up assessment are listed in Table 3. If a participant does not complete a follow-up assessment within 4 weeks of their initial reminder, they will be considered lost to follow up. However, their data will be retained and will be used in intent-to-treat analyses. We will make every effort to track and determine reasons for participant dropout including the unlikely possibility of an adverse event related to participation in this study.

7. SAFETY ASSESSMENTS

This is an extremely low risk study. However, participant safety will be monitored throughout the study by project staff. During Visits 1-6, study coaches will monitor participants withdrawal symptoms (if the participant quits tobacco), and provide assistance or referral to the patient's primary care physician.

7.1 Specification of Safety Parameters

The primary safety risk is the loss of privacy. However, all data will be stored on the secured ASHLine 2.0 and REDCap systems. We will be collecting usage data on the website, and participants could be concerned about the related lack of privacy.

If the participant quits smoking, s/he could experience withdrawal symptoms from nicotine cravings such as hunger, anxiety, restlessness, or sleep disturbance. Individuals who quit their addiction to tobacco products commonly experience these symptoms. Project coaches will be prepared to assist participants in handling these symptoms.

If a participant experiences adverse events as a result of using NRT, the coaches will be prepared to assist participants in handling these symptoms. In the event of an SAE, participants will be instructed to call 911 or schedule an appointment with their primary care provider. All AEs will be documented by project staff. Serious AEs will be reported to the University of Arizona IRB and the NCCIH Program Officer.

7.2 Methods and Timing for Assessing, Recording, and Analyzing Safety Parameters

Methods to assess, record, and analyze safety parameters will be ongoing throughout the study by study staff. The PI will be responsible for ongoing evaluation of the procedures used by the study coaches.

7.3 Adverse Events and Serious Adverse Events

An **adverse event (AE)** is generally defined as any unfavorable and unintended diagnosis, symptom, sign (including an abnormal laboratory finding), syndrome or disease which either occurs during the study, having been absent at baseline, or if present at baseline, appears to worsen. Adverse events are to be recorded regardless of their relationship to the study intervention.

A serious adverse event (SAE) is generally defined as any untoward medical occurrence that results in death, is life threatening, requires inpatient hospitalization or prolongation of existing hospitalization, results in persistent or significant disability/incapacity, or is a congenital anomaly.

It is possible that some questions about personal behaviors (e.g. smoking) might cause emotional discomfort to participants. Care will be taken to ensure that all participants understand that they may choose not to answer any question. Quitting smoking may result in physical symptoms (e.g., sleep disturbance) and changes in mood (e.g., irritability).

Participants who use NRT may experience adverse events. Most adverse events are rare. The most common adverse events are skin irritation and itching (nicotine patch), and mouth/throat soreness or ulcers (nicotine lozenges), vivid dreams and insomnia. Rarer, more serious adverse events include dizziness, headache, rapid heartbeat, and nausea. Participants will be screened for contraindications for use of NRT (e.g., recent heart attack, uncontrolled high blood pressure). Participants using NRT will be queried about AEs at each phone contact by coaches. Participants reporting AEs will be advised how to minimize side effects. Participants reporting SAEs will be advised to stop using the NRT and call 911 or their primary care physician. All participants will be given a study telephone number to contact the study staff if they have any concerns about an untoward medical event.

SSL and TLS security protocols will be used to protect all communications between the website and/or mobile devices and the project database. These protocols use certificate-based authentication to ensure that the user is communicating with the correct server. In addition, the protocols validate data and use public-key cryptography to guard against eavesdropping. Users will also be required to be authenticated by logging into the application with both their user name and password. This authentication data, as well as all other communications, will be transmitted securely using the SSL or TLS protocols.

7.4 Reporting Procedures

It is highly unlikely that any of the study procedures will cause an AE or SAE. Should an AE or SAE occur, ASHLine personnel and research study staff are trained to immediately report AEs connected to implementation of the intervention to [name] (co-I) or [name] (PI). [name] will report AEs to [name] who will keep a log of AEs and SAEs. In the event of an SAE, we will file a report with the University of Arizona (UA) IRB. As part of this process the UA IRB will determine if the event is directly related to project procedures, so that It can be determined if project procedures should be modified.

7.5 Followup for Adverse Events

[name] will monitor all AEs until resolved or considered stable up to the end of the study. Information about all AEs and SAEs will be provided in annual progress reports to UA IRB and NCI.

7.6 Safety Monitoring

The NCCIH requires that all Human Subjects research studies undergo independent monitoring, and NCCIH Program Officials will provide specific guidelines to the PI for the study.

Once approved by the UA IRB, the following aspects of the study and study conduct are monitored: all procedures to ensure conformity with the approved study protocol; unforeseen circumstance that might arise and affect participant safety; all reports of serious adverse events and defined in 38 CFR 46 (death, new or prolonged hospitalization, persistent or significant disability or incapacity; congenital anomaly

or birth defect); Other significant adverse events that lead to participant dropout, participant termination by the principal investigators, or termination of participation in the intervention.

8. INTERVENTION DISCONTINUATION

Participation in the study is voluntary. Participants may withdraw from the study at any time without penalty. Participants will continue to be followed with their permission if study intervention is discontinued (i.e., if they do not participate in all the coaching calls or use the website). Participants who wish to withdraw from all study activity will not be assessed at follow-up.

Possible reasons for participant withdrawal may include, but are not limited to, dissatisfaction with the intervention or study coaches/staff, lack of desire to quit smoking, or lack of time. No modifications to the study protocol will be permitted in terms of time spent with coaches, and the use of the study websites and audio files will be monitored.

Participants will be informed that: "You may refuse to participate in this study. If you decide to take part in the study, you may leave the study at any time. No matter what decision you make, there will be no penalty to you and you will not lose any of your usual benefits. Your decision will not affect your future relationship with the University of Arizona or the Arizona Smokers Help Line (ASHLine). If you are a student or employee at the University of Arizona, your decision will not affect your grades or employment status. If you are a patient at Banner University Medical Center, your decision will not affect your healthcare."

9. STATISTICAL CONSIDERATIONS

9.1 General Design Issues

This is a feasibility study using a two arm parallel randomized controlled design. We chose this design in order to run the definitive trial in miniature, so that we can reliably address the aim of our feasibility study, which is to give assurance that we can do the future study. Expanding upon this, we aim to answer: will we be able to recruit, randomize and retain participants?; are the trial procedures working?; are we using the correct measures?; what are the relevant variance components in order to design the future study; and is there any preliminary evidence that the intervention is effective?

We have defined feasibility outcomes as % completing the 6-session intervention program; % listening to the guided imagery audio files at least 5 times per week, % using the other website functions at least one time.

Our primary efficacy outcome is tobacco use. We hypothesize that the participants in the intervention group will have lower rates of tobacco use than in the control arm. Our secondary outcomes are dependence, cravings and self-efficacy. We hypothesize that the intervention group will have lower scores for dependence, cravings and higher score for self-efficacy, in comparison to the control arm.

Tobacco use. At baseline, and 8-weeks and 6-months post-enrollment follow-ups, we will collect tobacco use status using a series of questions that have been standardized

and employed in previous studies (Severson, [name], et al., 2008, [name] et al., 2007; Severson et al., 2000), and level of dependence using the the Fagerström Tolerance Nicotine Dependence scale (Fagerstrom & Schneider, 1989). At each visit, we will ask for participants' current tobacco use status. We will conduct biochemical validation using saliva test kit on all participants who report abstinence at the 6-month assessment and agree to perform a saliva test. Participants meeting these criteria will be mailed a saliva kit in the mail and then join a video chat with staff who will instruct the participant and monitor the collection of saliva and reading of the test strip. Participants will be offered \$25 for each sample.

Self-efficacy for quitting. We will measure self-efficacy for quitting smoking with items from the 15-item version of the Condiotte & Lichtenstein Confidence Questionnaire (Condiotte & Lichtenstein, 1981).

Cravings. All participants will be asked to rate their experience with withdrawal symptoms and cravings using items from the 5-item Shiffman rating scale (Shiffman, 2010) at baseline and each follow-up assessment.

9.2.2 Treatment Assignment Procedures

Randomization will be performed by REDCap using a randomization table created by a biostatistician who will have no contact with the participants. The allocation sequence will be automated, unpredictable, and concealed from study staff.

9.3 Definition of Populations

We will be using maximum likelihood based mixed models for all outcomes measured over time, using all available data. Mixed models are consistent with an intention to treat analysis due to their implicit imputation of missing data.

(Molenberghs et al., 2004). The per protocol population is defined as users who complete the 6-session intervention session.

9.4 Interim Analyses and Stopping Rules

No interim analyses or stopping rules are planned, as there are no potential safety issues, and because this is a feasibility study.

9.5 Outcomes

9.5.1 Primary Outcome

The primary efficacy outcome is tobacco cessation at 6 months.

The primary feasibility outcomes will be 50% of participants completing the 6-session intervention program; 50% of IIC participants listening to the guided imagery audio files at least 5 times per week, and 50% of participants using the website at least one time; and 75% of participants completed both follow-up assessments.

9.5.2 Secondary Outcomes

Secondary outcomes include number of quit attempts, number of cigarettes smoked, tobacco dependence, self-efficacy for quitting, and cravings. We will also explore the demographics of participants in the study compared to those of ASHLine callers in general.

9.5.3 Process and Exploratory Outcomes (Intervention Condition Participants)

All Participants

Website use. We collect usage data and can analyze use of all components of the site. Data most likely related to outcome will include, but not be limited to: (a) the length of time participants interact with the site; (b) the number of pages they visit within the site, and (c) the number of links they click on while using the site.

System usability. At both follow-up assessments, we will use Tullis and Stetson's (2008) 10-item adaptation of Brooke's widely used System Usability Scale (Brooke, 1996) to rate the usability of our website.

Imagery files use. These data will be collected automatically by the website. We will collect number of times and which imagery files were listened to completely, and if the participant created their own file.

Website use. We collect usage data and can analyze use of all components of the site. Data most likely related to outcome will include, but not be limited to: (a) the length of time participants interact with the site; (b) the number of pages they visit within the site, and (c) the number of links they click on while using

the site.

Imagery Intervention Condition Participants Only

Imagery files use. We will collect number of times and which imagery files were listened to completely, and if the participant modified and/or created their own file.

Imagery mastery. Ratings of imagery vividness and controllability will be measured weekly via the website in order to verify compliance with the protocol (Marks, 1973).

9.6 Data Analyses

Feasibility outcomes, including recruitment and dropout, will be described using frequencies and percentages, and 95% confidence intervals. Questionnaires will be scored according to developer instructions. Tobacco use outcome measures will use appropriate mixed models (linear for continuous outcomes and generalized linear with a logistic link for binary) using time categorically. Comparisons between the intervention and control group at 8 weeks and 6 months will be carried out using contrasts within these models. Mixed models are robust to missing outcome data (including dropout) and model misspecification, and are consistent with an intention to treat analysis (Bell and Fairclough, 2014; Mallinckrodt et al., 2004; Molenberghs et al., 2004). Mixed models will also be used to model self-efficacy, cravings, and consumer satisfaction, and to estimate intervention effects. Outcomes measured in the intervention group (e.g., imagery file use, website use), appropriate descriptive statistics will be computed, including means, standard deviations, ranges and frequencies/proportions. Linear regression and chi-square tests of trend will be used to assess the stability of the system usability and website/file use over time. We are underpowered to detect any subgroup analyses, but will conduct exploratory analyses in anticipation of the larger trial by including appropriate interactions within the mixed models. We will compare guided imagery use with tobacco outcome measures using linear regression in order to investigate a "dose-response" effect of the intervention. Demographics will be described with means, standard deviations, ranges and frequencies/proportions and will be explored as correlates for successful tobacco outcomes.

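### Section 9.6 names no baseline covariate for the 6-month abstinence comparison; pre-specifying adjustment for baseline dependence is an optional, low-cost improvement with modest gain

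*Combined protocol and SAP*

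**What the plan says.** Section 9.5.1 sets the target: "The primary efficacy outcome is tobacco cessation at 6 months". Section 9.6 gives the model for a binary tobacco outcome: "generalized linear with a logistic link for binary) using time categorically". It then describes the arm comparison: "Comparisons between the intervention and control group at 8 weeks and 6 months will be carried out using contrasts within these models".

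No covariate is listed for any efficacy model. The nearest text concerns demographics, which "will be explored as correlates for successful tobacco outcomes", and interactions for exploratory subgroup work. Neither adjusts the arm contrast, and neither mentions dependence.

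Section 6.2.2 provides for measuring "level of dependence using the the Fagerström Tolerance Nicotine Dependence scale", and Tables 3 and 4 both mark it at baseline. Its only stated analytic role is as a secondary outcome (Sections 9.1 and 9.5.2). On baseline smoking status, Section 6.2.2 says: "As all participants will be current smokers, there is no need for biochemical testing at baseline". Section 9.2.2 describes a randomization table and mentions no stratification or balancing factor.

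**The concern.** For a continuous outcome measured repeatedly, the baseline value of the outcome usually supplies the adjustment. Here it cannot, because abstinence at entry is essentially zero in both arms. Eligibility is any smoking in the past 30 days, so 7-day status might vary slightly, but it would carry little information. Dependence is one baseline measure that could do the job, and it is already collected.

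With 50 to 60 per arm and no stated stratification, the arms may differ by chance in dependence. If dependence predicts quitting, the unadjusted difference carries that imbalance. Because 9.6 is silent, the choice to adjust could also be made after the imbalance is seen.

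A second gap sits beside this. Section 9.1 says "At baseline, and 8-weeks and 6-months post-enrollment follow-ups, we will collect tobacco use status using a series of questions", and time is categorical, but 9.6 does not say whether the baseline visit, with almost no abstainers, is a level of time in the logistic model.

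**Working it through.** **Plan's own figures.** The plan states no power or precision for the arm difference in abstinence. Its 80% power (Section 9.2.1) is for continuous outcomes, so there is no matching figure to reproduce. Section 9.2.1 does claim a half-width of at most 1% for binary outcomes. At p = 0.5 and n = 50 it is 1.96 × √(0.25/50) = 13.9 points. That is a separate matter, but the 1% cannot serve as the yardstick here.

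**Inputs.** From the documents: 50 per arm (minimum), 60 (maximum), and 40 (50 less the plan's 20% dropout). Illustrative abstinence of 12% and 26% comes from the smaller imagery trial cited in Section 2.2; these are not planning values. Assumed: odds ratio for abstinence per 1 SD of dependence, from 1.0 (no effect) down to 0.5 or 0.4.

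**Size of chance imbalance.** The SD of the between-arm difference in a standardised score is √(2/n) = √(2/50) = 0.20, so the 95% limit is 1.96 × 0.20 = 0.39 SD. P(|imbalance| > 0.3 SD) = 2 × (1 − Φ(0.3/0.20)) = 0.13.

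**Effect of that imbalance.** To first order, shift ≈ |ln OR| × p(1 − p) × imbalance.
- OR 0.8, p = 0.12: 0.223 × 0.1056 × 0.392 = 0.9 points.
- OR 0.5, p = 0.26: 0.693 × 0.1924 × 0.392 = 5.2 points.

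Simulation (about 3,000 trials per setting; one logistic model at 6 months, with and without the score) at 50 per arm, across 12% v 12%, 12% v 26% and 26% v 26%, gives 0.9–1.3 points at OR 0.8, 1.5–2.2 at OR 0.7 and 2.5–4.9 at OR 0.5. After adjustment, no more than about 0.4 points remain.

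**Gain from adjustment**, 12% v 26%, 50 per arm:

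| OR per SD | Variance ratio of risk difference (adj/unadj) | SE of log OR, unadj → adj | Power, unadj → adj | Shift at 95% imbalance (points) |
|---|---|---|---|---|
| 1.0 | 1.013 | 0.569 → 0.575 | 40.5% → 41.0% | 0.1 |
| 0.8 | 1.004 | 0.569 → 0.578 | 41.6% → 43.0% | 1.2 |
| 0.7 | 0.998 | 0.569 → 0.582 | 40.8% → 42.0% | 2.0 |
| 0.6 | 0.983 | 0.570 → 0.589 | 40.5% → 43.2% | 2.5 |
| 0.5 | 0.954 | 0.572 → 0.602 | 41.6% → 43.9% | 3.5 |

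The lowest ratio at 50 per arm in the three rate settings is 0.92 (26% v 26%, OR 0.5). Over 40 to 60 per arm and ORs of 1.0 to 0.4 at 12% v 26%, the ratio runs from about 0.89 to 1.03 and the power change from about -1 to +5 points.

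**Yardstick.** The unadjusted 95% half-width for the arm difference at n = 50 is 1.96 × √(p₁(1 − p₁)/50 + p₂(1 − p₂)/50): 12.7 points at 12% v 12%, 15.1 at 12% v 26% and 17.2 at 26% v 26%.

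**The two effects are one.** At 26% v 26% and OR 0.5, the imbalance contributes an SD of 4.9/1.96 = 2.5 points to a standard error of 17.2/1.96 = 8.8. Its share of the variance is (2.5/8.8)² = 8%, which matches the ratio of 0.92. The imbalance shift and the lost precision should not be counted as two harms.

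**The case against.** A reader might infer that the plan has chosen an unadjusted model. The text does not support that: 9.6 speaks of appropriate mixed models, gives no full formula, and neither lists nor excludes covariates. What stands is silence.

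A reader might also infer that chance imbalance biases the result. It does not. It is part of randomization error, and the unadjusted interval already covers it; a shift of 1 to 5 points sits inside a half-width of about 13 to 17.

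Nor is the precision free. On the log-odds scale of the planned model, the standard error rises with adjustment. The variance gain appears on the risk difference, and only if dependence is prognostic; if it is not, there is a slight loss.

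Dependence is not the only candidate either: self-efficacy, cravings, expectancy and prior use of cessation resources are also collected at baseline.

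Finally, little hangs on the comparison. Section 9.2.1 makes feasibility the primary objective and says the later trial will not be sized from pilot effects. All of this stands, and it limits the weight of the point.

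It does not remove it. Section 9.1 still asks for preliminary evidence of effect and treats this study as a small-scale rehearsal of the later trial, so the model used here may be carried forward. Stating the adjustment in advance also closes a choice that is now open.

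**Conclusion.** The point holds as an optional improvement, not as an error in the plan. Section 9.6 leaves baseline adjustment of the 6-month abstinence comparison unspecified, although a suitable score is already collected and baseline smoking status can do little or nothing.

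The benefit is modest: most of a 1 to 5 point shift removed at the 95% limit of imbalance (50 per arm, OR 0.8 to 0.5 per SD), a risk-difference variance between about 3% larger and 11% smaller, and a power change of about -1 to +5 points (OR 1.0 to 0.4).

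All of these rest on assumed prognostic strength and borrowed abstinence rates. The simulation used one time point without a random intercept; a random intercept would not remove an imbalance between arms. A claim that the planned analysis loses material precision, or that its estimate cannot be trusted, would go beyond what the documents support.

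**What to change.** Add to Section 9.6 wording such as:

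> The 6-month abstinence comparison will be fitted to the post-baseline assessments and adjusted for the baseline Fagerström score as a continuous covariate. The effect will be reported as a standardised risk difference with a 95% confidence interval (variance by bootstrap or delta method, to be stated). The unadjusted estimate will be given as a sensitivity analysis.

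This also settles whether the baseline visit enters the logistic model. The standardised risk difference avoids comparing conditional and unadjusted odds ratios, which are on different scales.

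No new data are needed. The costs are one extra parameter, a small loss of precision if dependence turns out not to be prognostic, and some extra analysis work: if the estimate comes from the mixed model, standardising means averaging over the random effects.
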